13.5.6 Safety Analyses

Safety will be assessed by clinical review of all relevant parameters including AEs, SAEs, laboratory values, vital signs, physical exam and ECG results. Unless specified otherwise, the safety analyses will be conducted for the safety population. An interim safety analysis is planned following the completion of Cycle 1 for the first 20 patients enrolled in the Phase 2 expansion phase and will utilize a Data Safety Monitoring Board.

Summary tables and listings will be provided for all reported Treatment Emergent Adverse Events (TEAEs), defined as AEs that start on or after the first administration of study treatment. The reported AE term will be assigned a standardized preferred term using the current version of the Medical Dictionary for Regulatory Activities (MedDRA).

TEAEs will be summarized based on the number and percentage of patients experiencing the event by MedDRA system organ class (SOC) and preferred term (PT). In the event a patient

experiences repeat episodes of the same AE, then the event with the highest severity grade and strongest causal relationship to study treatment will be used for purposes of incidence tabulations.

Tabular summaries will be provided for:

- all TEAEs
- TEAEs by relationship to study treatment and maximum severity grade
- TEAEs with action of study treatment delayed/interrupted or dose reduced
- TEAEs with action of study treatment discontinued
- SAEs

For the escalation phase, the observed DLT rate in each dose cohort will be calculated by the crude proportion of patients who experienced DLT with a 2-sided 95% exact binomial CI.

All deaths that occur on study (defined as during treatment or within 30 days of treatment discontinuation) will be reported in a patient listing, which will include the primary cause of death and the number of days between the date of the last dose of study drug and death.

Hematology and serum chemistries will be summarized in a descriptive manner by calculating the mean, standard deviation, median, and range as follows:

- baseline value
- minimum post baseline value
- maximum post baseline value
- average post baseline value
- last post baseline value

Laboratory values will be assigned toxicity grades when available using the NCI Common Terminology Criteria for Adverse Events (CTCAE) version 4.03. Directional shifts in laboratory toxicity grades (comparing baseline grade with worst post-baseline grade) will be analyzed using standard shift tables, presenting number and proportion of patients and their maximum grade shift. For analytes without a toxicity grading scale, the shift table will present directional shifts from baseline to above or below the laboratory standard normal range using the maximum increase and/or decrease observed throughout the course of treatment/observation.

Vital signs will be summarized in a descriptive manner by calculating the mean, standard deviation, median, and range in the same manner described for laboratory values.

ECG results will be listed and summarized in terms of the number and percentage of patients with abnormal and normal findings, as reported by the Investigator, at the time points assessed (screening and EOT).

Prior and concomitant medications will be coded to generic term using the current version of the World Health Organization Drug Dictionary and will be tabulated and listed by patient.

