10.2.7 Adverse Events

AEs, as defined in [Section 12.2.1](#), are to be documented from the time of informed consent through 30 days post-last dose, with the exception of AESIs with atezolizumab, which must be

documented through 90 days following cessation of treatment, or 30 days after the initiation of a new anticancer therapy, whichever is earlier.

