12.4 Serious Adverse Event Reporting Procedures

SAEs will be collected and recorded throughout the study period, beginning with the signing of the informed consent form through 90 days after the last dose of study drug, or after the end of the study if thought to be related to entinostat or the combination. All SAEs must be reported to Syndax or its representative within 24 hours of discovery or notification of the event. Initial SAE information and all amendments or additions must be recorded on a Serious Adverse Event Report Form and provided to Syndax or its representative. The SAE reporting procedure is provided in the Study Manual.

For all deaths, available autopsy reports and relevant medical reports should be provided to Syndax or its representative. If a patient is permanently withdrawn from the study because of an SAE, this information must be included in the initial or follow-up Serious Adverse Event Report Form as well as the EOS eCRF.

The Investigator should notify the IRB or EC of SAEs occurring at the site and other AE reports received from Syndax, in accordance with local procedures and statutes.

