12.4.3 Adverse Events of Special Interest with Atezolizumab

Selected non-serious and SAEs are also known as AESI, Adverse Events of Special Interest. As noted in [Section 9.6](#), DLTs will also be captured as AESI. AESI must be recorded as such in

the AE eCRF, completing the same fields as for Serious Adverse Events, and reported within 24 hours to the Sponsor. Such events must be documented through 90 days following cessation of treatment, or 30 days after the initiation of a new anticancer therapy, whichever is earlier.

Sponsor Contact information can be found in the Study Manual.

Toxicities associated or possibly associated with atezolizumab treatment should be managed according to standard medical practice. Additional tests, such as autoimmune serology or biopsies, should be used to determine a possible immunogenic etiology.

Although most immune-mediated adverse events observed with immunomodulatory agents have been mild and self-limiting, such events should be recognized early and treated promptly to avoid potential major complications. Discontinuation of atezolizumab may not have an immediate therapeutic effect and, in severe cases, immune-mediated toxicities may require acute management with topical corticosteroids, systemic corticosteroids, mycophenolate, or TNF- α inhibitors.

The investigator should consider the benefit-risk balance for a given patient prior to further administration of atezolizumab. Atezolizumab should be permanently discontinued in patients with life-threatening immune-mediated adverse events.

For the management of other adverse events associated with the atezolizumab not provided below, refer to the Atezolizumab IB. Patients should be assessed for possible AESIs prior to each dose of study medication. Laboratory results should be evaluated and patients should be asked for signs and symptoms suggestive of an immune-related event. Patients who develop an AESI thought to be immune-related should have additional testing to rule out other causes. If laboratory results or symptoms indicate a possible immune-related AESI, then additional testing should be performed to rule out other causes. If no other cause is found, then it is assumed to be immune-related.

The following conditions may be suggestive of an autoimmune disorder and are considered AESI for this study:

- Pneumonitis
- Colitis
- Endocrinopathies: Diabetes mellitus, Pancreatitis, Adrenal Insufficiency, Hyperthyroidism, and Hypophysitis
- Vasculitis

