12.4.6 Protocol Deviations Due to an Emergency or Adverse Event

Departures from the protocol will be determined as allowable on a case-by-case basis and only in the event of an emergency. The Investigator or other physician in attendance in such an emergency must contact the Medical Monitor as soon as possible to discuss the circumstances of the emergency.

The Medical Monitor, in conjunction with the Investigators, will decide whether the patient should continue to participate in the study. All protocol deviations and corresponding remediation plan will be tracked in the TRIO Clinical Trial Management System.

Period of Observation:

The table below summarizes the different periods of observation of AE, SAE, AESI with Atezolizumab and Pregnancy/Lactation.

Type of Event	AE	SAE	AESI with Atezolizumab	Pregnancy/Lactation
Reporting period	From consent until 30 days after the end of the treatment	From consent until 90 days after the last dose of study treatment for all SAEs, and any time after the end of study for SAEs believed related to entinostat or the combination	From consent until 90 days after the last dose of study treatment, or 30 days after the initiation of a new anticancer therapy, whichever is earlier	From consent until 120 days after the last dose of study treatment or 30 days following the discontinuation of the study treatment in case of the start of a new anticancer therapy Note: all patients becoming pregnant must be followed up

				to the completion / termination of the pregnancy.
Reporting Timelines to the Sponsor	Entered into the clinical database on an ongoing basis	Within 24 hours	Within 24 hours	Within 24 hours

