6.10 Treatment Emergent Adverse Events (TEAEs)

TEAEs is defined as AEs that start on or after the first administration of study treatment or AEs that start before the first administration of study treatment but worsened after study treatment is initiated.

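### The treatment-emergent AE definition has no end, so the all-TEAE, maximum-grade and Grade 3/4 tables mix on-treatment events with serious events on the next therapy

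*Protocol*

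**What the plan says.** Protocol 13.5.6 defines TEAEs by onset: "defined as AEs that start on or after the first administration of study treatment". SAP 6.10 widens this to "AEs that start on or after the first administration of study treatment or AEs that start before the first administration of study treatment but worsened" once treatment has begun. Neither gives a last day, and no other section supplies one.

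The upper limit is then whatever the collection rules allow:

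- **AEs in general** (protocol 10.2.7): they "are to be documented from the time of informed consent through 30 days post-last dose". The observation-period table in 12.4.6 agrees: "From consent until 30 days after the end of the treatment".
- **SAEs** (protocol 12.4): "through 90 days after the last dose of study drug, or after the end of the study if thought to be related". The 12.4.6 table has "From consent until 90 days after the last dose of study treatment for all SAEs", and SAEs after the study only if believed related to entinostat or the combination. New anticancer therapy does not close the window.
- **AESIs** (protocol 12.4.3): 90 days, "or 30 days after the initiation of a new anticancer therapy, whichever is earlier".

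Protocol 9.9 lets patients go on to standard of care at the investigator's discretion once study treatment stops. SAP 10.9.2 and 11.1 plan TEAE tables for all events, by maximum grade and for Grade 3/4, with separate tables by relationship to each drug. SAP 10.9.2 states that the SAE table and the summary of AEs leading to death are not restricted to TEAEs. SAP 5.4.2 ties the interim and primary safety analyses to the PFS cut-offs.

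**The concern.** An SAE on day 60 after the last dose, during next-line chemotherapy, meets both TEAE definitions. It enters the all-cause TEAE tables of the randomised arm, at its grade. A non-serious Grade 3 event in the same patient on the same day, if not an AESI, is not collected. From day 31 to day 90 these tables thus record events largely by seriousness, and many of those events may belong to another regimen.

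The protocol recognises the problem for AESIs, where new therapy shortens the window, but not for SAEs. Its listing of on-study deaths in 13.5.6 stops at 30 days, so a 30-day boundary is already in use there.

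At stake is how the Phase 2 between-arm safety tables are read. Safety is cut at the PFS event counts, when the arms are expected to differ in how many patients have stopped treatment, so next-line events need not be spread evenly.

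**Working it through.** **Text check.** Set side by side, the definitions have no end and the collection windows are unequal. The mixing of windows follows from that alone, without a model.

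**Inputs from the documents.** Median PFS 4 months (control) and 7 months (entinostat), 9 months of accrual plus 9 of follow-up, 35 patients per arm, looks at about months 12 and 18 (SAP 5.2.2, protocol 13.1.2 and 13.2); one month is 30.4375 days.

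**Assumptions.** Exponential PFS, uniform accrual, treatment stops at PFS failure, every patient then starts new therapy, deaths treated as survivors. The event rate λ is not in the documents; 0.10 per month is assumed, with a range of 0.05 to 0.20.

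**Check on the model.** The plan gives no figure for the TEAE window, so only its PFS model can be reproduced. With 60 events, hazard ratio 0.57 and one-sided 0.1, the Schoenfeld formula gives 81.5% power, or 80.4% with an O'Brien-Fleming-type look at 75% information; the plan states 80%. Expected events at months 12 and 18 are 42.2 and 56.8, against the stated approximate 45 and 60.

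**Step 1: share of patients more than d months past stopping, at cut-off c.** With h = ln 2 / median (0.1733 and 0.0990):

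P(d) = 1 − [exp(−h(c−9−d)) − exp(−h(c−d))] / (9h)

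At c = 12 and d = 30/30.4375 = 0.986:

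- Control: 1 − (0.7054 − 0.1483)/1.560 = 0.643
- Entinostat: 1 − (0.8192 − 0.3360)/0.891 = 0.458

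(Where c−9−d is negative, the integral runs only over patients enrolled early enough.)

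**Step 2: person-months in days 31-90 per patient.** Integrate P(d) from 0.986 to 90/30.4375 = 2.957.

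| Cut-off | Share past day 30, control vs entinostat | Person-months, days 31-90 | Ratio |
|---|---|---|---|
| Month 12 | 64% vs 46% | 1.13 vs 0.79 | 1.43 |
| Month 18 | 87% vs 70% | 1.67 vs 1.32 | 1.27 |
| Month 30 | 98% vs 91% | 1.93 vs 1.77 | 1.09 |

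Starting the next therapy on day 14, 30 or 60 gives ratios of 1.42-1.45 at month 12 and 1.26-1.28 at month 18.

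**Step 3: patients newly counted.** The tables count a patient once per category. A day 31-90 event adds her only if she had none before:

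E[ exp(−λ(S + 0.986)) × (1 − exp(−λW)) ]

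Here S is time on treatment and W the observed part of days 31-90. The same λ applies before and after day 30.

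| λ per month | Month 12, control vs entinostat | Month 18 |
|---|---|---|
| 0.05 | 4.6% vs 3.1% | 6.3% vs 4.8% |
| 0.10 | 7.4% vs 5.0% | 9.7% vs 7.1% |
| 0.20 | 10.0% vs 6.6% | 12.2% vs 8.5% |

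At 0.10 the differences are 35 × 0.024 = 0.8 patient and 35 × 0.026 = 0.9 patient. At 0.20 they are 35 × 0.034 = 1.2 and 35 × 0.037 = 1.3.

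**Step 4: whole window, first dose to the end of collection.** Mean treatment time is the accrual average of [1 − exp(−h(c−e))]/h, with e the enrolment time; add the integral of P(d) from 0 to the end of the window.

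| Window | Month 12, control vs entinostat | Ratio | Month 18 | Ratio |
|---|---|---|---|---|
| To day 90 | 5.8 vs 6.4 months | 0.91 | 7.7 vs 9.4 months | 0.82 |
| To day 30 | 4.7 vs 5.6 months | 0.84 | 6.0 vs 8.1 months | 0.75 |

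**The case against.** A reader might infer that the open window inflates control and so hides an entinostat excess. The documents do not support that. Step 4 shows that entinostat has the longer total window under the plan's own assumptions. With equal event hazards, its crude incidence would still be the higher one. Closing the window at day 30 makes observation time less equal, not more.

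A reader might also infer that next-line events are labelled as drug-related. They are not: treatment-emergent describes timing. Causality is assessed separately (protocol 12.3), and the related-TEAE tables take such an event only if the investigator calls it related. Nor do unlimited late SAEs leak in, since after the 90-day window only those thought related are collected.

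Further points stand:

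- The direction assumes that control stops first. An excess toxicity-stopping hazard on entinostat of 0.1733 − 0.0990 = 0.074 per month would remove the gap, and more would reverse it.
- In the all-TEAE row, almost nobody would be newly counted.
- The planned listings carry AE dates and the start of later therapy, so a split can be made from data already collected.
- No hypothesis test, sample size or power depends on this.

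None of this supplies an end to the definition, or removes next-line serious events from the all-cause maximum-grade and Grade 3/4 tables.

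**Conclusion.** The point holds as one of attribution and unequal windows. Both TEAE definitions are open-ended, and the SAE window runs to day 90 whether or not new therapy has begun. Control accrues more day 31-90 time at the two PFS-driven cut-offs, and the imbalance fades to a ratio of 1.09 by month 30.

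The effect on counts is modest: under 1 patient of 35 between arms at an assumed 0.10 events per month, and about 1.3 at 0.20. These figures rest on the plan's PFS medians, on stopping at PFS failure, on everyone surviving to start new therapy, and on an event rate the documents do not give. A net bias in either direction is not shown. This is a cheap improvement worth making, not a threat to the trial's conclusions.

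**What to change.** Before unblinding, so that the window is not chosen with results in hand:

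1. In protocol 13.5.6 and SAP 6.10, define a TEAE as an AE that starts or worsens from first dose to 30 days after last dose, or to the start of new anticancer therapy if earlier. This also aligns the two documents on worsening events.
2. Tabulate later SAEs and AESIs, to day 90, separately by arm, flagged by whether new therapy had begun.
3. Split the SAE and AEs-leading-to-death tables of SAP 10.9.2 the same way. They are not TEAE-based, so step 1 alone leaves them unchanged.
4. Show exposure time by arm beside the crude incidences, because the shorter window makes observation time less equal.
5. Keep every event in the listings. Align the death listings: protocol 13.5.6 stops at 30 days, while SAP 10.9.3 lists all deaths.

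The cost is wording in two documents, one added table and a split of two others. Data collection, sample size and power do not change. The downside is that late immune-related events move from the main TEAE table to the separate one.

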13.5.7 Pharmacokinetic and Antidrug Antibody Analyses

A population PK analysis will be used to describe the PK of entinostat. The effects of patient factors (e.g., demographics, clinical chemistries, disease) on entinostat PK will be evaluated. In addition, the relationship between entinostat exposure parameters and indicators of safety will be assessed.

Specific details for these analyses as well as analyses of trough atezolizumab levels and anti-atezolizumab antibodies will be provided in a separate analysis plan.

13.5.8 Correlative Analyses

Immune correlate values will be summarized in a descriptive manner. For immune correlates measured on a continuous scale, the number of patients with no missing data, mean, either the standard error or standard deviation, median, 25th percentile (first quartile), 75th percentile (third quartile), minimum, and maximum values will be presented. For discrete data, the frequency and percent distribution will be presented. The Wilcoxon signed rank test (for within-treatment comparisons) and Wilcoxon rank sum test (for between-treatment comparisons) will be used to identify any systematic changes in biomarker levels from baseline. Additionally, the correlation among the various initial immune correlate values may be assessed by calculating Spearman's correlation coefficient. Analysis of covariance models may be used to explore the relationship between changes in immune correlates and selected measures of antineoplastic activity (e.g., maximum change from baseline in the sum of product diameters in measurable lesions). The association among the various immune correlates and clinical outcomes (data permitting) may be explored using heat map and other data visualization techniques.

14. REGULATORY OBLIGATIONS

This clinical study was designed and shall be implemented and reported in accordance with the protocol, the ICH Harmonized Tripartite Guidelines for Good Clinical Practice, with applicable local regulations (including European Directives 2001/20/EC and 2005/28/EC and the US Code of Federal Regulations Title 21), and with the ethical principles laid down in the Declaration of Helsinki.

14.1 Informed Consent

A template informed consent form is provided for the Investigator to prepare the informed consent document to be used at his or her site. Updates to the template will be communicated by letter from Syndax or designee to the Investigator.

Before a patient's participation in the clinical study, the Investigator is responsible for obtaining written informed consent from the patient or legally acceptable representative after adequate explanation of the aims, methods, anticipated benefits, and potential hazards of the study and before any protocol-specific screening procedures are conducted or any investigational products are administered. The acquisition of informed consent should be documented in the patient's medical records, and the informed consent form should be countersigned by the person who conducted the informed consent discussion (not necessarily an Investigator). The original signed informed consent form should be retained in accordance with institutional policy, and a copy of the signed consent form should be provided to the patient or legally acceptable representative.

14.2 Institutional Review Board (IRB)/Ethics Committee (EC)

A copy of the protocol, proposed informed consent form, other written patient information, and any proposed advertising material must be submitted to the IRB/EC for written approval. A copy of the written approval of the protocol and informed consent form, in addition to other essential regulatory documents per [Section 14.3](#), must be received by Syndax or designee before recruitment of patients into the study and shipment of study drug.

The Investigator must submit and obtain approval from the IRB/EC for all subsequent protocol amendments and changes to the informed consent document. The Investigator should notify the IRB/EC of deviations from the protocol or SAEs occurring at the site and other AE reports received from Syndax, in accordance with local procedures.

When required, the Investigator will be responsible for obtaining annual IRB/EC renewals throughout the duration of the study. Copies of the Investigator's submission and the IRB/EC continuance of approval must be sent to Syndax or its representative.

14.3 Pre-study Documentation Requirements

The Investigator is responsible for providing the following documents to Syndax or its representative before study initiation can occur:

- Signed and dated protocol signature page (Investigator's Agreement).
- Completed Food and Drug Administration form 1572 or equivalent per local regulatory requirements.
- Curricula vitae of Principal Investigator and all sub-investigators (updated within 12 months).
- Copy of the IRB/EC approval of the protocol, consent form, and patient information sheet.
- IRB/EC composition or written statement that the board is in compliance with regulations.
- Laboratory normal ranges and documentation of laboratory certification (or equivalent).
- Signed Clinical Trial Agreement between Syndax or its representative and the authorized representative at the institution, or investigator if applicable.
- Completed Financial Disclosure statements for the Principal Investigator and all sub-investigators.

14.4 Patient Confidentiality

The Investigator must ensure that the patient's confidentiality is maintained. In the eCRFs or other study documentation submitted to Syndax or its representative, patients should be identified only by their initials (unless prohibited by local regulatory guidelines) and a patient ID number. Patient samples should be identified only by the patient ID number. Documents that are not for submission to Syndax or its representative (i.e., signed informed consent forms) should be kept in strict confidence by the Investigator.

In compliance with federal guidelines and applicable local regulations, it is required that the Investigator and institution permit authorized representatives of the company, of the regulatory agency(s), and the IRB/EC direct access to review the patient's original medical records for verification of study-related procedures and data. Direct access includes examining, analyzing, verifying, and reproducing any records and reports that are important to the evaluation of the study. The Investigator is obligated to inform and obtain the consent of the patient to permit named representatives to have access to his/her study-related records without violating the confidentiality of the patient.

